Postpartum hemorrhage (PPH), which accounts for 30% of all direct maternal deaths, is the single most important cause of maternal morbidity and mortality across the globe (1) and is a focus of attention of national organizations such as the Council for Patient Safety in Womens Health in recent years. Yet, there remains a paucity of data on the appropriate management of non-acute postpartum anemia. Packed red blood cells (pRBC) transfusion may be a lifesaving treatment for acute hemorrhage, but it is also widely used after PPH for non-acute, stable anemia (2). Postpartum anemia is associated with clinical consequences including fatigue and symptoms of depression (3,4). A low postpartum hemoglobin (Hb) is the most important commonly cited reason to prescribe RBC transfusions (5). The indication for RBC transfusion, however, is not to increase postpartum Hb level, but to reduce morbidity and improve the health-related quality of life. It is common practice in obstetrics to offer a transfusion of pRBCs to women with a Hb value less than 7 g/dL (hematocrit less than 20%) and to symptomatic women with even higher hemoglobin levels (2). Transfusions were historically initiated with 2 units of pRBCs, and this remains the case on many labor and delivery units across the country, including at the Hospital of the University of Pennsylvania. However, there is increasing concern about adverse effects and costs of current transfusion practice. The most recent recommendation from the American Association of Blood Banks (AABB) for a stable patient is to begin with 1 unit and reassess (6). The American College of Obstetricians and Gynecologists, in the newly released 2017 practice bulletin on postpartum hemorrhage, has included the AABBs statement, endorsing the use of single-unit transfusion (7). While surgical data has successfully demonstrated that liberal blood transfusion increases morbidity and mortality in comparison to restricted transfusion (8), no trials have been performed in obstetrics to demonstrate superiority of a single-unit transfusion protocol. In addition, a qualitative study in Australia looking at provider practice and perception regarding single- versus multiple- unit transfusion protocols after a similar national recommendation demonstrated wide variation. To some providers, single-unit transfusions had lower perceived utility and multiple-unit transfusions were perceived to improve maternal-infant bonding and infectious outcomes. In contrast, others believed that single-unit transfusions reduced infection and transfusion reaction risk while having the same desired efficacy (9).

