In our population, it is unlikely to approach a patient who would be unable to consent. If a patient is unable to provide informed consent as determined by an informal assessment by her provider, she will not be eligible for this study.

2. Waiver of Consent

Waiver or Alteration of Informed Consent*

No Waiver Requested

Minimal Risk*

Impact on Subject Rights and Welfare*

Waiver Essential to Research*

Additional Information to Subjects

Written Statement of Research*

No

If no written statement will be provided, please provide justification

The following documents are currently attached to this item:

There are no documents attached for this item.

Risk / Benefit

Potential Study Risks

Given each of these patients has been determined to need a blood transfusion, minimal risk exists in receiving single-unit versus multiple-unit protocols. Multiple-unit transfusion is our current standard of care. The risk of the single-unit protocol is that the patient may require a prolonged length of stay to receive blood more slowly (one unit at a time) as well as slower relief of symptoms. In addition, more blood may expose a patient to increased likelihood of infection, reaction, or antibody development.

Potential Study Benefits

It is unclear whether single-unit or multiple-unit transfusion is more beneficial to the patient. Single-unit transfusion protocol may expose the patient to decreased total units, thereby decreasing the risk of transfusion reaction, antigen exposure, and infection via the blood product. There is a large benefit to society in terms of determining whether single-unit transfusion is superior to our current standard of care as it could lead to decreased use of a scarce medical resource, donated blood.

Alternatives to Participation (optional)

Outside of the study, it will be provider dependent whether a patient receives 1 or 2 units of blood.

Data and Safety Monitoring

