The study PI will be responsible for ensuring the ongoing quality and integrity of the research study. An adverse event (AE) is any symptom, sign, illness or experience that develops or worsens in severity during the course of the study. Intercurrent illnesses or injuries should be regarded as adverse events. Abnormal results of diagnostic procedures are considered to be adverse events if the abnormality: results in study withdrawal is associated with a serious adverse event is considered by the investigator to be of clinical significance. Need for additional blood products, transfusion reactions, and prolonged length of stay will not be considered adverse events as they represent expected issues related to the single-unit blood transfusion protocol. We plan to start recording adverse events at the time of randomization until the follow up visit. Information on all adverse events will be obtained by review of the medical record and recorded immediately in the source document, and also in the appropriate adverse event module of the case report form (CRF). The PI will review all adverse events weekly. All adverse events occurring during the study period will be recorded. The clinical course of each event will be followed until resolution, stabilization, or until it has been determined that the study intervention or participation is not the cause. Serious adverse events that are still ongoing at the end of the study period will be followed up to determine the final outcome. Any serious adverse event that occurs after the study period and is considered to be possibly related to the study intervention or study participation will be recorded and reported. The relationship of each adverse event to the study procedures will be characterized by the principal investigator as definitely related, probably related, possibly related, unlikely or unrelated. The Investigator will promptly notify the Penn IRB of all on-site unanticipated, Adverse Events that are probably or definitely related to the study procedures. Other unanticipated problems related to the research involving risk to subjects or others will also be reported promptly. Written reports will be filed using the HS-ERA and in accordance with the Penn IRB timeline of 10 working days. If an AE has not resolved at the time of the initial report and new information arises that changes the investigators assessment of the event, a follow-up report including all relevant new or reassessed information (e.g., concomitant medication, medical history) should be submitted to the IRB. The investigator is responsible for ensuring that all SAEs are followed until either resolved or stable.

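### The safety plan excludes all transfusion reactions, however serious, from adverse events for a reason that does not fit them, so a serious reaction would bypass PI review and follow-up

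*Combined protocol and SAP*

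**What the plan says.** All of the AE rules are in the protocol's Data and Safety Monitoring section. It defines an AE broadly, as any symptom, sign, illness or experience that appears or worsens during the study, and then removes three items: need for additional blood products, transfusion reactions and prolonged stay. For the last two the sentence reads "transfusion reactions, and prolonged length of stay will not be considered adverse events as they represent expected issues related to the single-unit blood transfusion" protocol.

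The same section sets out what happens to an AE:

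- It is "recorded immediately in the source document, and also in the appropriate adverse event module of the case report form (CRF").
- On the timing of review, the text is: "The PI will review all adverse events weekly".
- On relatedness, it is: "The relationship of each adverse event to the study procedures will be characterized by the principal investigator", on a five-level scale.
- Its course is followed, and serious events are followed until resolved or stable.
- The IRB is promptly told of AEs that are unanticipated and probably or definitely related. Other unanticipated problems involving risk are also reported promptly.

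On risk, Potential Study Risks states: "The risk of the single-unit protocol is that the patient may require a prolonged length of stay to receive blood more slowly". It adds slower symptom relief, and then says that "more blood may expose a patient to increased likelihood of infection, reaction, or antibody development". Potential Study Benefits says: "Single-unit transfusion protocol may expose the patient to decreased total units, thereby decreasing the risk of transfusion reaction". The Background reports a divided view among providers in a qualitative study, in which "others believed that single-unit transfusions reduced infection and transfusion reaction risk while having the same desired efficacy".

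Transfusion reactions are also listed under Secondary outcome variable(s), as part of maternal morbidity.

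**The concern.** Every participant is enrolled in order to be transfused, and reactions are a harm of transfusion that the protocol itself names. Excluding them from AEs, with no limit on seriousness, removes them from the only scheduled safety review in the available text. The reason given attaches them to the single-unit protocol, which is the arm the protocol elsewhere suggests may have fewer of them. It offers no ground at all for excluding them in the multiple-unit arm.

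What is at stake is oversight while the trial runs. A serious reaction would not be put before the PI each week, rated for relatedness, or followed to resolution under the AE rules. Listing reactions as a secondary outcome does not replace this, because that listing names no reviewer and no time of review.

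**Working it through.** The plan states no figure on this point to reproduce. The check compares the text of the sections.

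**1. Does the exclusion have a limit?** The general AE definition would cover a reaction, so the exclusion sentence alone takes it out. That sentence gives no grade, no seriousness threshold and no arm. The section does not define a serious AE separately, so no definition brings a serious reaction back in. Prolonged stay is excluded in the same sentence, so a longer stay caused by a reaction does not bring it back either.

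**2. Does the stated reason fit each excluded item?**

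| Excluded item | What the risk and benefit sections say | Reason fits? |
|---|---|---|
| Additional blood products | Not listed as a risk; follows from giving blood one unit at a time | Yes, by inference |
| Prolonged stay | Named as a risk of the single-unit protocol | Yes |
| Transfusion reactions | Linked to more blood; possibly fewer with single-unit | No |

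The planning figures under Study duration point the same way. With 33 per group and the assumed means of 1.9 and 1.68 units per person:

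- multiple-unit arm: 33 × 1.9 = 62.7 units
- single-unit arm: 33 × 1.68 = 55.4 units
- relative reduction: (1.9 − 1.68) / 1.9 = 0.22 / 1.9 = 11.6%

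With the 1.75 target given under Design, the reduction is (1.9 − 1.75) / 1.9 = 0.15 / 1.9 = 7.9%. These are design assumptions, not results. They show only that the plan itself anticipates less exposure to blood in the single-unit arm.

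**3. What follows for a serious reaction?** AE recording, weekly review, relatedness rating and serious-event follow-up are all written for AEs or serious AEs. An event declared not to be an AE enters none of them. This is one consequence with four practical effects.

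**4. Is expectedness handled elsewhere?** Yes. Prompt IRB notice of AEs is already limited to unanticipated ones. Expectedness can justify not expediting a report; it does not explain why the PI should not record, review or follow the event.

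**5. How many are covered?** 33 + 33 = 66 participants, matching the planned enrolment. The documents give no reaction rate, so no event count can be derived.

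**The case against.** The strongest reply is that expected does not mean increased. A reaction can be less frequent with single-unit transfusion and still be foreseeable, so the two sections need not contradict each other; naming only the single-unit protocol may be loose drafting. The lower risk is also hypothesis and provider opinion, not established fact. This stands in part: reactions are foreseeable whenever blood is given. It does not rescue the rule, because the reason as written ties them to one arm, and foreseeability is already dealt with at the IRB notification step.

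A second reply is that a serious reaction might still be recorded, through its symptoms or complications, or by reading the exclusion as covering only ordinary reactions. That is possible, but it relies on staff reading a limit into a sentence that has none, and different readings would give inconsistent recording. The route for other unanticipated problems also stays open in principle. Its use is uncertain for a class declared expected, and it leads to the IRB, not to weekly review or follow-up.

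Three further points stand as limits. Reactions are a secondary outcome, so they should still be counted. The procedures file, the consent form and the IRB response letter are listed as attachments but are not available, and they may address reactions. With accrual of about 3 patients a month and investigators taking part in consent and randomization, the practical loss may be small. None of these supplies the missing rule in the text that can be read.

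Finally, the fix would send mild reactions through the AE process as well as serious ones. That is true. The extra work is small, since reactions must already be captured for the secondary outcome, and it avoids having to write a new seriousness threshold.

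**Conclusion.** The concern holds. The exclusion of reactions is explicit and unlimited, its stated reason does not fit them, and under the text as written a serious reaction in either arm would miss the AE module, the weekly PI review, the relatedness rating and serious-event follow-up. The rule covers all 66 planned participants; the number of events affected is unknown.

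Confidence is high for the wording of the rule and medium for its practical effect, which assumes that staff follow the sentence literally and that the unavailable attachments do not override it. No bias, no effect on the primary outcome and no loss of the secondary comparison is claimed. This should be corrected, as a gap in safety oversight that is cheap to close.

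**What to change.** Delete the words *transfusion reactions* from the exclusion sentence in Data and Safety Monitoring. Reactions in both arms then go through the existing AE recording, weekly PI review, relatedness rating and serious-event follow-up. Leave the restriction of prompt IRB notice to unanticipated events as it is. The reason given in the sentence then covers only additional blood products and prolonged stay, which agrees with Potential Study Risks. Check that the attached procedures and consent form say the same.

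The cost is a two-word deletion and a few more AE forms. No new scale, grading or data source is needed: the relatedness scale is already in the section, and reactions must already be captured as a secondary outcome. No treatment rule changes.

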
Is this study funded by an industry sponsor?

Status of contract

The following documents are currently attached to this item:

There are no documents attached for this item.

Multi-Site Research

Other Sites

No other sites

Management of Information for Multi-Center Research

The following documents are currently attached to this item:

There are no documents attached for this item.

Protocol

Abstract

Postpartum hemorrhage (PPH), which accounts for 30% of all direct maternal deaths, is the single most important cause of maternal morbidity and mortality across the globe and is a focus of attention of national organizations such as the Council for Patient Safety in Womens Health in recent years. Yet, there remains a paucity of data on the appropriate management of non-acute postpartum anemia. It is common practice in obstetrics to offer a transfusion of packed red blood cells (pRBCs) to women with a hemoglobin (Hb) value less than 7 g/dL (hematocrit less than 20%) and to symptomatic women with even higher hemoglobin levels. Although transfusions were historically initiated with 2 units of pRBCs, the most recent recommendation from the American Association of Blood Banks (AABB) for a stable patient is to begin with 1 unit and reassess. However, while surgical data has successfully demonstrated that liberal blood transfusion increases morbidity and mortality in comparison to restricted transfusion, no randomized controlled trials have been performed in obstetrics to demonstrate superiority of a single-unit transfusion protocol. We propose a randomized, controlled trial in non-acute postpartum anemia comparing single-unit versus multiple-unit transfusion by total numbers of units transfused and maternal morbidity with the hypothesis that single-unit transfusions can reduce the number of units transfused without increasing maternal morbidity.

Objectives

Overall objectives

We propose a randomized, controlled trial in non-acute postpartum anemia comparing single-unit versus multiple-unit transfusion by total numbers of units transfused and maternal morbidities.

Primary outcome variable(s)

To determine if a single-unit pRBC transfusion protocol in non-acute postpartum anemia can reduce total number of units transfused compared to a multiple-unit pRBC transfusion protocol.

Secondary outcome variable(s)

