To determine if there is a difference between single-unit and multiple-unit transfusion protocols in maternal morbidity, including postpartum infections, length of stay, and transfusion reactions. To determine if there is a difference between single-unit and multiple-unit transfusion protocols in breastfeeding rates at hospital discharge and 6 weeks postpartum. To determine if there is a difference between single-unit and multiple-unit transfusion protocols in Edinburgh Postnatal Depression Scale, Multidimensional Fatigue Inventory, and Maternal Attachment Inventory score at 6 weeks postpartum.

Background

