In order to determine our expected sample size, we assessed our baseline data (15). During this time period, the culture at our institution was that if the decision was made to proceed with transfusion, generally 2 units of pRBCs were given. Over a 3 month period in 2015, 612 patients delivered, of which 30 received pRBC transfusions (4.9%). 11 of these transfusions occurred prior to the 12 hour blood count, which may indicate a more acute need for transfusion. Some of those patients may have also received additional units in the non-acute setting after stabilization and thus would still qualify to participate in this study. In the whole group of transfused patients, a total of 74 units of pRBCs were transfused, at an average of 2.5 units per person transfused. Excluding those transfused in the first 12 hours postpartum, 36 units of pRBCs were transfused among 19 patients at an average of 1.9 units per person transfused (with a standard deviation [SD] of 0.3). Thus, over one year, we would expect to see approximately 72 patients requiring non-acute postpartum transfusion. Our expected sample size to have 80% power to demonstrate a reduction in number of blood products used per person from 1.9 to 1.68 with a SD of 0.5, assuming an alpha of 5%, would be 33 patients per group. If 50% of patients agreed to participate, we estimate it will take 2 years to achieve this sample size. We then expect it will take an additional year to analyze and publish our data. For each study participant, they will be involved in the study from the time of consent until their 4-9 week postpartum visit. In order to reduce burden to patients, we plan to combine our postpartum survey instruments with the routine postpartum visit.

Resources necessary for human research protection

Describe research staff and justify that the staff are adequate in number and qualifications to conduct the research. Describe how you will ensure that all staff assisting with the research are adequately informed about the protocol and their research related duties. Please allow adequate time for the researchers to conduct and complete the research. Please confirm that there are adequate facilities for the research.

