Through the Council for Patient Safety in Womens Health, the primary investigator won a National Improvement Challenge Award for work in postpartum hemorrhage. This award totaled \$3000 designated for future work in this realm. We plan to utilize this funding for patient compensation as a part of this trial. Given we ask the patient to return for a study visit to complete survey data, we plan to compensate patients for the time and effort involved in participating in this study. We plan to provide the patient with \$25 on discharge date from delivery hospitalization and \$25 at the time of the 4-9 week postpartum End of Study Visit once the survey instruments are complete. This will be provided in the form of a Visa giftcard.

Study Procedures

Suicidal Ideation and Behavior

Does this research qualify as a clinical investigation that will utilize a test article (ie- drug or biological) which may carry a potential for central nervous system (CNS) effect(s)?

No

Procedures

See attached document.

The following documents are currently attached to this item:

Procedures (smartbloodprotocolforirbv2.pptx)

Deception

Does your project use deception?

No

International Research

Are you conducting research outside of the United States?

No

Analysis Plan

Baseline and demographic characteristics will be summarized by standard descriptive statistics (including mean and standard deviation for continuous variables such as age and standard percentages for categorical variables such as gender). We will use T tests to compare number of units transfused between our single-unit and multiple-unit transfusion protocols.

The following documents are currently attached to this item:

There are no documents attached for this item.

Data confidentiality

- x **Paper-based records will be kept in a secure location and only be accessible to personnel involved in the study.**
- x **Computer-based files will only be made available to personnel involved in the study through the use of access privileges and passwords.**

Prior to access to any study-related information, personnel will be required to sign statements agreeing to protect the security and confidentiality of identifiable information.

- x **Wherever feasible, identifiers will be removed from study-related information.**

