Privacy refers to the person's desire to control access of others to themselves. Privacy concerns people, whereas confidentiality concerns data. Describe the strategies to protect privacy giving consideration to the following: The degree to which privacy can be expected in the proposed research and the safeguards that will be put into place to respect those boundaries. The methods used to identify and contact potential participants. The settings in which an individual will be interacting with an investigator. The privacy guidelines developed by relevant professions, professional associations and scholarly disciplines (e.g., psychiatry, genetic counseling, oral history, anthropology, psychology).

Potential participants will be identified by their physician and asked if they would be willing to speak with research staff. Only if a patient agrees will they be approached by research staff. Once enrolled in the study, the only contact with research staff will be to schedule the postpartum follow up by telephone.

Data Disclosure

Will the data be disclosed to anyone who is not listed under Personnel?
De-identified data may be released to statistical support staff if needed.

Data Protection*

x Name Street address, city, county, precinct, zip code, and equivalent geocodes
 
x All elements of dates (except year) for dates directly related to an individual and all ages over 89
 
x Telephone and fax number Electronic mail addresses Social security numbers
 
x Medical record numbers Health plan ID numbers Account numbers Certificate/license numbers Vehicle identifiers and serial numbers, including license plate numbers Device identifiers/serial numbers Web addresses (URLs) Internet IP addresses Biometric identifiers, incl. finger and voice prints Full face photographic images and any comparable images Any other unique identifying number, characteristic, or code None

--

Does your research request both a waiver of HIPAA authorization for collection of patient information and involve providing Protected Health Information ("PHI") that is classified as a "limited data set" (city/town/state/zip code, dates except year, ages less than 90 or aggregate report for over 90) to a recipient outside of the University of Pennsylvania covered entity?
No

Tissue Specimens Obtained as Part of Research*

Are Tissue Specimens being obtained for research?
No

Tissue Specimens - Collected during regular care*

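### Adverse events are taken from the medical record alone up to the 4-9 week visit, and postpartum infection has no stated source, so post-discharge infections managed elsewhere may be missed

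*Combined protocol and SAP*

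**What the plan says.** - **Source and window.** Data and Safety Monitoring states "Information on all adverse events will be obtained by review of the medical record" and "We plan to start recording adverse events at the time of randomization until the follow up visit". It names no other source. The same section defines an adverse event broadly and undertakes to record every one in the study period.
- **Carve-out.** That section also says "Need for additional blood products, transfusion reactions, and prolonged length of stay will not be considered adverse events".
- **Outcomes.** Secondary outcome variable(s) lists "maternal morbidity, including postpartum infections, length of stay, and transfusion reactions". It gives no definition, time window or data source for infection.
- **Hypothesis.** The Abstract proposes that "single-unit transfusions can reduce the number of units transfused without increasing maternal morbidity". No margin is given, and the Analysis Plan describes a test only for units transfused.
- **The visit.** Study duration says "we plan to combine our postpartum survey instruments with the routine postpartum visit". Under Subject compensation, the second payment is made "at the time of the 4-9 week postpartum End of Study Visit once the survey instruments are complete". Completing the surveys is the only content stated for the visit.
- **Research contact.** Subject Privacy says that after enrolment "the only contact with research staff will be to schedule the postpartum follow up by telephone".
- **Not shown.** The study procedures and the survey instruments are separate attachments, listed under Procedures and General Attachments.

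**The concern.** The recording window runs well past discharge, but the only named source is the chart. A woman treated for infection or readmitted at another facility leaves no entry in the delivery hospital's record unless someone there is told and writes it down. Followed as written, the plan has no step that asks her, although she is due to attend a compensated visit at 4-9 weeks.

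Missing events equally in both arms is often treated as harmless. It is not harmless when part of the hypothesis is that morbidity does not rise. Lost events pull the absolute difference towards zero and also narrow its confidence interval, so the result looks more reassuring because less was seen. Infection is a live question in this trial. Potential Study Risks raises greater infection risk with more blood, while Background reports that some providers believe multiple units improve infectious outcomes.

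**Working it through.** **Inputs from the documents.** There are 33 women per group (Study duration and Accrual), allocated 1:1. The documents give no infection rate, no share of infections arising after discharge and no share of care received elsewhere. They state no figure for morbidity or its capture, so there is none to reproduce. The 33 was sized on units transfused and is used here only as the planned enrolment. By the usual two-sided formula, its stated inputs give 2 × (1.96 + 0.8416)² × 0.5² / 0.22² = 81.1, that is 82 per group, which is a separate matter.

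**Assumptions.** Let f be the share of infections arising after discharge. Let e be the share of those managed elsewhere and never charted. Both are taken as equal by arm.

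**Step 1: effect on the comparison.** Capture is s = 1 − f × e. Each observed risk is s × p. The observed risk difference is s × (p2 − p1), and the observed risk ratio is (s × p2)/(s × p1) = p2/p1, unchanged.

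| f | e | s | A true 10-point excess appears as |
|---|---|---|---|
| 0.5 | 0.3 | 1 − 0.15 = 0.85 | 8.5 points |
| 0.5 | 0.5 | 1 − 0.25 = 0.75 | 7.5 points |
| 1.0 | 0.3 | 0.70 | 7 points |
| 1.0 | 0.5 | 0.50 | 5 points |

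The last two rows need every infection to arise after discharge. They are an outer bound.

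**Step 2: event counts.** At an assumed risk of 5-10%, 33 women give 33 × 0.05 = 1.65 to 33 × 0.10 = 3.3 events per arm. With s of 0.75-0.85, between 1.65 × 0.75 = 1.24 and 3.3 × 0.85 = 2.81 are captured.

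**Step 3: interval width.** With equal true risks of 10%, and q = 0.10 × s, the 95% half-width is 1.96 × √(2q(1 − q)/33). This is 14.5 points at full capture, 13.1 at 80% and 11.5 at 60%.

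**Step 4: power.** Power is Φ((RD − 1.96 × SE0)/SE1), with SE0 = √(2p̄(1 − p̄)/33) and SE1 = √((p1(1 − p1) + p2(1 − p2))/33). For 10% versus 20% at full capture, SE0 = 0.0879 and SE1 = 0.0870, so Φ((0.10 − 0.1723)/0.0870) = Φ(−0.83) = 20%.

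| True risks | Full capture | 80% | 60% |
|---|---|---|---|
| 10% v 20% | 20% | 17% | 13% |
| 5% v 10% | 12% | 10% | 8% |

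Fisher's exact test is weaker still: 12%, 8% and 4% for the first row.

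**The case against.** Several stronger readings are tempting, and the documents do not support them.

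- **That all morbidity outcomes rest on the chart alone.** The record-review sentence covers adverse events. Transfusion reactions, additional blood products and prolonged stay are expressly outside that category. Reactions in hospital and the length of the delivery stay would ordinarily be in the delivery record. For infection, the source is unstated rather than stated to be the chart.
- **That outside infections are certainly missed and the women are never asked.** The surveys are combined with a routine clinical visit, where an interim infection could be mentioned, charted and then found. The text does not limit the medical record to one hospital. The attachments might contain such a question. What stands is that the instruments the protocol describes measure depression, fatigue and attachment, and that charting at a routine visit is not specified as a means of ascertaining outcomes.
- **That a 10-point excess would appear as 5-7 points.** This applies a post-discharge loss to every infection, including those diagnosed before discharge.
- **That the bias serves only one conclusion.** The secondary aims are framed as looking for a difference. Potential Study Benefits anticipates less infection with single units, and attenuation would hide that benefit too.

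The strongest objection is consequence. With power of roughly 8-20% in these scenarios, 33 per arm cannot establish that morbidity is not increased, whatever the capture. That is right: sample size is the tighter limit. It does not remove the gain in safety capture, nor the reason to avoid a bias that a few questions could reduce.

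Self-report also carries its own risk. No blinding is described, and the recruitment script tells women that one versus two units is the question, so reporting could differ by arm.

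**Conclusion.** The point holds for post-discharge infections and readmissions. As written, adverse events come from the record only, and the infection outcome has no stated source, so events managed at another facility may be missed. Under equal capture the absolute difference shrinks by the factor s and the risk ratio does not move. A reading of no increase in morbidity becomes easier to reach on the absolute scale.

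The size cannot be computed from the documents. The figure of 7.5-8.5 points for a true 10-point excess rests on two assumptions: half of infections arise after discharge, and 30-50% of those are seen elsewhere. If capture differs by arm, neither the direction nor the unchanged risk ratio is assured.

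This is a cheap improvement. It would not make the trial large enough to support a claim about morbidity, and a reader should not infer that it would.

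**What to change.** 1. Define postpartum infection, its time window and its data source.
2. Unless the attached survey already does so, add a short set of questions at the End of Study Visit, worded identically for both arms: infection diagnosed or antibiotics taken, emergency visit, readmission, and transfusion at any facility since discharge. If the attachment already asks, cite it under Data and Safety Monitoring.
3. Amend the source sentence there to medical record review plus participant report at the End of Study Visit. Align Subject Privacy with whoever collects the answers.
4. Seek records for every positive answer. Use record-confirmed infections for the main secondary comparison, and add unconfirmed self-reports as a sensitivity analysis.
5. Record any outside transfusion as units transfused, not as an adverse event, in keeping with the existing exclusion.

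**Cost.** About one case report form page at a visit already planned and compensated, plus the record requests. Some reports will not be confirmable, and self-reporting may differ by arm, which is why confirmed events come first. Women who miss the visit will still depend on the record.
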